[figure not shown]

# TABLE OF ABBREVIATIONS

AE	Adverse event	
AESI	Adverse event of special interest	
ATC	Anatomical therapeutic chemical	
BID	Twice per day	
BTK	Bruton's tyrosine kinase	
COVID-19	Coronavirus disease 2019	
CR	Complete response	
CRF	Case report form	
CSP	Clinical study protocol	
CSR	Clinical study report	
CTCAE	Common Terminology Criteria for Adverse Events	
DLT	Dose-limiting toxicity	
DOR	Duration of response	
ECI	Event of clinical interest	
ECOG	Eastern Cooperative Oncology Group	
ECG	Electrocardiogram	
FLIPI	Follicular Lymphoma International Prognostic Index	
FL	Follicular Lymphoma	
GELF	The Groupe d'Etude des Lymphomes Folliculaires	
IPD	Important protocol deviation	
IV	Intravenous	
KM	Kaplan-Meier	
LDH	Lactate dehydrogenase	
MedDRA	Medical Dictionary for Regulatory Activities	
MZL	Marginal zone lymphoma	
MRD	Minimum residual disease	
ORR	Overall response rate	
OS	Overall survival	
PD	Pharmacodynamic / progressive disease	
PFS	Progression-free survival	
PK	Pharmacokinetic	
PO	Orally	

PR	Partial response
PT	Preferred term
QD	Once per day
R/R	Relapsed/refractory
SAE	Serious adverse event
SAP	Statistical analysis plan
SD	Standard deviation / stable disease
SOC	System organ class
TEAE	Treatment-emergent adverse event
TTNT	Time-to-next treatment
ULN	Upper limit of normal
WHO	World Health Organization

#### 1. INTRODUCTION

The purpose of this statistical analysis plan (SAP) is to provide detailed methodology for summary and statistical analyses of the safety and efficacy endpoints that have been outlined within Parts 2 and 3 of Clinical Study Protocol (CSP) Amendment 6 for Study ACE-LY-003, which is entitled "An Open-label, Phase 1b/2 Study of Acalabrutinib Alone or in Combination Therapy in Subjects with B-cell Non-Hodgkin Lymphoma" dated March 5, 2020. This SAP will be used to support a clinical study report (CSR).

#### 2. OBJECTIVES

#### 2.1 Part 2 (Marginal Zone Lymphoma)

#### 2.1.1 Primary Objective

 To characterize the activity of acalabrutinib alone or in combination with rituximab in subjects with relapsed/refractory (R/R) marginal zone lymphoma (MZL), as measured by overall response rate (ORR)

## 2.1.2 Secondary Objectives

- To characterize the safety of acalabrutinib alone or in combination with rituximab in subjects with R/R MZL
- To evaluate the activity of acalabrutinib alone or in combination with rituximab in subjects with R/R MZL, as measured by duration of response (DOR), progression-free survival (PFS), and overall survival (OS)

# 2.1.3 Exploratory Objectives

[figure not shown]
# 2.2 Part 3 (Follicular Lymphoma)

#### 2.2.1 Primary Objective

• To characterize the safety of acalabrutinib in combination with rituximab and lenalidomide in subjects with R/R follicular lymphoma (FL)

#### 2.2.2 Secondary Objectives

 To characterize the activity of acalabrutinib in combination with rituximab and lenalidomide in subjects with R/R FL as measured by ORR, DOR, PFS, and OS

#### 3. STUDY OVERVIEW

## 3.1 Study Design

#### Part 2

This part of the study is a Phase 2, multicenter, open-label, study to be conducted at approximately 38 centers. Up to 40 subjects with R/R MZL will be enrolled. At the time of CSP Amendment 6, the decision was made to close Cohort 2 (one subject was enrolled on Cohort 2).

- Cohort 1: Acalabrutinib 100 mg orally (PO) twice per day (BID) administered approximately 12 hours apart (BID dosing=200 mg total daily dose).
- Cohort 2: Acalabrutinib 100 mg PO BID administered approximately 12 hours apart (BID dosing=200 mg total daily dose), plus rituximab 375 mg/m2 intravenous (IV) on Days 1, 8, 15, and 22 of Cycle 1 and Day 1 of Cycles 2 through 6.

#### Part 3

This part of the study is a dose-finding, Phase 1b, multicenter, open-label study to be conducted at approximately 38 centers. Approximately 26 to 32 subjects with R/R FL will be enrolled and treated with acalabrutinib, rituximab, and lenalidomide. Once a safe and tolerable dose of lenalidomide has been established, 14 subjects (as part of the 26 to 32 subjects total) will be treated on the 3 drugs at that dose of lenalidomide.

• Acalabrutinib 100 mg PO BID administered approximately 12 hours apart (BID dosing=200

mg total daily dose), until disease progression or an unacceptable toxicity occurs.

- Rituximab 375 mg/m2 IV administered on Days 1, 8, 15, and 22 of Cycle 1, and Day 1 of
  every cycle starting at Cycle 2 through Cycle 6, followed by 10 additional doses of
  maintenance rituximab every other cycle beginning with Cycle 8 for subjects who have not
  progressed.
- Lenalidomide will start at 15 mg PO once per day (QD) for the first 6 subjects in Cycle 1.
   Doses up to 20 mg PO QD will be explored. Lenalidomide will be administered on Days 1 through 21 of a 28-day cycle.

Six subjects are planned to be enrolled initially and treated with acalabrutinib, rituximab, and lenalidomide (15 mg PO QD) in Cycle 1. At the end of the cycle, subjects will be evaluated for dose-limiting toxicities (DLTs) on a rolling basis.

- If there are ≥2 subjects with DLTs on 15 mg of lenalidomide QD, the dose of lenalidomide will be reduced to 10 mg QD, and 6 more subjects are planned to be enrolled at this reduced dose of lenalidomide.
  - If there are ≥2 subjects with DLTs at the end of Cycle 1 on 10 mg lenalidomide QD, enrollment will close.
  - If there are <2 of 6 subjects with DLTs, then approximately 14 additional subjects will be enrolled and treated with lenalidomide 10 mg QD for Cycles 1 through 12.
- If there are <2 of 6 subjects with DLTs on 15 mg QD, 6 additional subjects are planned to be enrolled to receive an increased dose of lenalidomide at 20 mg QD.
  - o If there are ≥2 subjects with DLTs, the dose of lenalidomide will be reduced back to 15 mg QD. Approximately 14 more subjects will be added to complete enrollment at the 15-mg QD dose.
  - If there are <2 of 6 subjects with DLTs, 20 mg of lenalidomide will be the dose used for Cycles 2 through 12. Approximately 14 more subjects will be added to complete enrollment.

Note: Subjects will be evaluated for DLTs at the end of the first cycle, on a rolling basis, when they complete a cycle of treatment.

For both parts, twenty-eight days is one cycle. Treatment with acalabrutinib may be continued until confirmed disease progression or an unacceptable drug-related toxicity occurs. Please refer to CSP Appendices 5 and 6 for the complete schedule of assessments.

# 3.2 Sample Size

#### Part 2

Part 2 will enroll up to 40 subjects in Cohort 1 that will provide data for an initial assessment of safety and efficacy of acalabrutinib treatment. Sample size is not based on statistical power consideration. At the time of CSP Amendment 6, the decision was made to close Cohort 2 (per CSP Amendment 4, Cohorts 1 and 2 were planned to enroll 20 subjects each). One subject was enrolled in Cohort 2 before it was closed.

#### Part 3

A total of approximately 26 to 32 subjects are to be enrolled in Part 3. This sample size will provide adequate data for an initial assessment of safety and efficacy of acalabrutinib treatment in combination with lenalidomide and rituximab. This sample size is not based on statistical power consideration.

#### 4. STUDY ENDPOINTS

# **4.1 Efficacy Endpoints**

Standardized response and progression criteria have been established for lymphoma (Cheson et al. 2014); assessments of efficacy in this study will be based on these criteria. For Parts 2 and 3, the efficacy endpoints include:

- ORR
- DOR
- PFS
- OS

#### 4.2 Safety Endpoints

The safety of acalabrutinib alone, or in combination with rituximab, or in combination with rituximab and lenalidomide, will be characterized by adverse event (AE) type, frequency, severity, timing of onset, duration, and relationship to study drug (acalabrutinib, rituximab, and/or lenalidomide); serious adverse events (SAEs); and AEs leading to dose interruption of rituximab, reduction of acalabrutinib and/or lenalidomide, or withholding or discontinuation of acalabrutinib, lenalidomide, and/or rituximab.

For consistency of interpretation, AEs will be coded using Medical Dictionary for Regulatory

Activities (MedDRA), and the severity of AEs and laboratory abnormalities will be graded using the Common Terminology Criteria for Adverse Events (CTCAE) version 5.0. Standard definitions for seriousness will be applied (see CSP Section 6.2).

# 4.3 Pharmacokinetic (PK) and Pharmacodynamic (PD) Parameters

#### Part 2

No PK analysis will be performed in Part 2. The PD analyses will be detailed in a separate analysis plan: the effect of acalabrutinib on biologic markers of BTK function will be evaluated; molecular profiling of tumor, blood, and bone marrow, when available (including but not limited to BTK mutation), will be performed.

#### Part 3

Sparse acalabrutinib PK samples will be collected and analyzed to investigate the relationship between acalabrutinib and its active metabolite (ACP-5862) concentration and response. The PD analyses will be detailed in a separate analysis plan: the effect of acalabrutinib on biologic markers of BTK function will be evaluated; molecular profiling of tumor, blood, ctDNA, and bone marrow when available (including but not limited to BTK mutation), will be performed.

#### 5. ANALYSIS POPULATIONS

#### **5.1 All-Treated Population**

The all-treated population is defined as all subjects who receive ≥1 dose of any study drug (acalabrutinib, rituximab, or lenalidomide). Demographic and baseline characteristics, efficacy analyses, and safety analyses will be performed on the all-treated population unless otherwise specified.

#### 5.2 Efficacy-Evaluable Population

The efficacy-evaluable population will include all subjects in the all-treated population who have ≥1 response assessment after the first dose of any study drug (i.e. overall response not "unknown" or missing). Sensitivity analyses for efficacy will be carried out on the efficacy-evaluable population.

# 5.3 PK Population

The PK population will be defined for Part 3 only and will include all subjects who receive ≥1 dose

of acalabrutinib and have ≥1 PK measurement after the first dose of acalabrutinib. PK analyses will

be carried out on the PK population.

6. GENERAL CONVENTIONS

Part 2 and Part 3 analyses will be performed separately. Unless otherwise specified, the analyses

outlined in this SAP will be performed for both Part 2 and Part 3.

Continuous data will be summarized using descriptive statistics (number of observations, mean,

standard deviation, median, minimum, and maximum). Frequencies and percentages will be used

for summarizing categorical data. Confidence intervals, when presented, will generally be

constructed at the 2-sided 95% level. For binomial variables, the exact method will be employed

unless otherwise specified.

Calculation of time to event or duration of event endpoints will be based on the study day of the

event or censoring date rather than visit number or visit label. Missing efficacy or safety data will

not be imputed unless otherwise specified.

The following rules will be used for the days to months/years conversion:

1 month=30.4375 days

• 1 year=365.25 days

All summaries will be presented by treatment arm and total unless otherwise specified. Data will be

presented in data listings by treatment arm and subject number.

**6.1 Definitions** 

6.1.1 Definition of Baseline and Post-Baseline Value

Baseline is defined as the last measurement taken prior to the first dose of any study drug. A post-

baseline value is defined as a measurement taken after the first dose of any study drug.

For assessments on the day of first dose where time is not captured, a nominal pre-dose indicator,

if available, will serve as sufficient evidence that the assessment occurred prior to first dose.

Assessments on the day of first dose where neither time nor a nominal pre-dose indicator are

captured will be considered prior to first dose if such procedures are required by the protocol to be

conducted before first dose.

## 6.1.2 Definition of Study Day

Study Day 1 is defined as the first dose date of any study drug. For visits (or events) that occur on or after first dose date, study day is defined as (date of visit [event] – first dose date + 1). For visits (or events) that occur prior to first dose date, study day is defined as (date of visit [event] – first dose date).

#### 6.1.3 Definition of Prior and Concomitant Medication

For the purpose of inclusion in prior and/or concomitant medication summaries, incomplete medication start and stop dates will be imputed as detailed in Section 6.2. Based on imputed start and stop dates:

- Prior medications are defined as medications with a start date occurring before the date of first dose of any study drug.
- Concomitant medications are defined as medications that:
  - Had start date on or after the first dose date of study drug and either within 30 days after the last dose date (latest of any study drug), or before the first dose date of subsequent anticancer therapy, whichever is earlier, or
  - Had start date before first dose date of any study drug and were either ongoing or had a stop date on or after first dose date.
- Medications that meet the criteria for both prior and concomitant medication will be classified as both prior and concomitant medication.
- Medications with completely missing start and stop dates will be considered as both prior and concomitant medications.

# **6.1.4 Prior and Subsequent Anticancer Therapy**

For the purpose of inclusion in the prior and/or subsequent anticancer therapy summaries, incomplete medication start dates will be imputed as detailed in Section 6.2. Based on imputed start dates:

- Prior anticancer therapies are defined as therapies with a start date before the date of first dose date of any study drug.
- Subsequent anticancer therapies are defined as therapies with a start date after the date of last dose (latest of any study drug).

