3.8 WITHDRAWAL OF SUBJECTS FROM STUDY TREATMENT

Subjects may be withdrawn from study treatment for the following reasons:

- Progressive disease
- Completed treatment
- Start of alternative anticancer therapy
- Adverse event
- Pregnancy
- Investigator's decision
- Subject's withdrawal of consent from the study
- Decision by sponsor to terminate the study
- Subject lost to follow-up
- Death
- Other

Subjects who have received ≥1 dose of study drug and discontinue study therapy will continue to be followed on study for follow-up of safety (Section 4.3), disease, time-to-next therapy, and long-term follow-up (Section 4.4) unless they withdraw consent for further follow-up. The date the subject is withdrawn from study treatment or from the study and the reason for discontinuation will be recorded and described on the appropriate eCRF.

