# **6.2.1 Adverse Events, Concomitant Medications, Prior/Subsequent Anticancer Therapies, Initial Diagnosis**

Imputation of partial dates will be made for AE onset and stop dates, start and end dates of concomitant medication, start date of prior/subsequent anticancer therapy, and date of initial diagnosis. If dates are completely missing, no imputation will be made. For any partial date with missing year, no imputation will be made.

The general rule for imputation is:

- If only day is missing, then the 15th of the month will be used.
- If only year is present, then June 30th will be used.

If such imputed date for initial diagnosis or prior anticancer therapy is on or after date of first dose date of any study drug, then date of first dose – 1 will be used. If such imputed date for subsequent anticancer therapy is before date of last dose (latest of any study drug), then date of last dose + 1 will be used.

If the imputed date is for an AE start date and is in the same year and month as but before the first dose date of any study drug, then the first dose date will be used, or if the imputed AE start date is after the AE end date, then the AE end date will be used. If the imputed date is for an AE start date and is in the same year and month as but after the last dose date (latest of any study drug) + 30 days, then the last dose date + 30 days will be used.

If the imputed date is for an AE end date and is after the death date, then the death date will be used, or if the imputed AE end date is before the AE start date, then the AE start date will be used.

ACE-LY-003 Parts 2-3 Statistical Analysis Plan Version 1.0: 31Mar2022

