#### 7.6.1 Overall Response Rate

Best overall response is defined as the best disease outcome over all response assessments on or before the initiation of subsequent anticancer therapy. Best overall response categories include CR, PR, SD, and PD. The number and percentage of subjects in each best overall assessment category will be presented by treatment arm. ORR will be defined as the proportion of subjects who achieve a CR or PR according to the Lugano Classification for NHL (Cheson et al. 2014), as assessed by investigators. ORR will be calculated, and the corresponding 2-sided 95% confidence interval will be derived.

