**Table 1. PFS Censoring** 

Situation Date of Event or Censoring Outcome			
Situation 1: PFS events include death or first disease progression as assessed by			
investigator that occurred at or prior to the earliest of data analysis cutoff date,			
alternative cancer therapy start date, and discontinuation from study (and not			
immediately following ≥2 consecutively missed visits where CT scan was required).			
Date of event is defined as follows:			
Death before first disease assessment	Date of death	Event	
INV-PD or death before study exit or	Earlier date of INV-PD or death	Event	
data cutoff			
Situation 2: All other cases not meeting	ng 'Situation 1' will be censored as	follows:	
No baseline assessment	First dose date of any study	Censored	
No baseline assessment	drug	Censored	
No adequate* post-baseline	First dose date of any study	Censored	
assessment		Censored	
	drug		
No INV-PD or death at the time of data	Date of last adequate* INV	Censored	
cutoff	assessment before data cutoff		
No INV-PD or death before lost to	Date of last adequate* INV	Censored	
follow-up or study exit	assessment before lost to		
	follow-up or study exit		

No INV-PD or death before start of	Date of last adequate* INV	Censored
subsequent anticancer therapy	assessment before start of	
	subsequent anticancer therapy	
INV-PD or death immediately after two	Date of last adequate* INV	Censored
INV-PD or death immediately after two or more consecutively missed visits	Date of last adequate* INV assessment before missing two	Censored

Abbreviation: INV=investigator

PFS will be calculated as date of disease progression or death (censoring date for censored subjects) – date of first dose of any study drug + 1.

Kaplan-Meier methods will be used to estimate the event-free curves by arm and corresponding quantiles (including the median). The proportion of subjects who are progression-free and the corresponding 95% CI will be estimated based on KM method at select timepoints by treatment arm.

If at least 1 subject has an event of death (and without progression prior to death) due to COVID-19, a sensitivity analysis will be conducted to assess for the potential impact of deaths due to COVID-19. Subjects with death related to COVID-19 infection (and without progression prior to death) will be censored at their last evaluable assessment prior to their COVID-19 related death date.

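### The SAP's only definition of subsequent anticancer therapy requires all study drugs to have stopped, so lymphoma therapy started on treatment neither closes the response window nor triggers the PFS/DOR censoring row

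*SAP*

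**What the plan says.** SAP 6.1.4 sets up two classes. Prior: "Prior anticancer therapies are defined as therapies with a start date before the date of first dose date of any study drug". Subsequent: "Subsequent anticancer therapies are defined as therapies with a start date after the date of last dose (latest of any study drug". The section opens by tying itself to the therapy summaries: "For the purpose of inclusion in the prior and/or subsequent anticancer therapy summaries, incomplete medication start dates will be imputed". No other section defines either term.

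The efficacy sections then rely on the word *subsequent*:

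- SAP 7.6.1: "Best overall response is defined as the best disease outcome over all response assessments on or before the initiation of subsequent anticancer therapy". ORR is the share of subjects with CR or PR.
- SAP Table 1, Situation 2, has one row for new therapy. It applies to subjects without progression or death before a subsequent anticancer therapy and censors them at the last adequate assessment before it.
- SAP 7.6.2 takes its DOR censoring from Table 1.

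Table 1, Situation 1, uses different wording. Its list of limits on when an event can count includes "alternative cancer therapy start date, and discontinuation from study (and not"; the parenthesis goes on to missed scans. The SAP does not define alternative cancer therapy.

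For partial dates, SAP 6.2.1 adds: "If such imputed date for subsequent anticancer therapy is before date of last dose (latest of any study drug", the date becomes the day after last dose.

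The current protocol censors PFS and DOR at the last tumor assessment before alternative anticancer therapy (Section 5.4) and attaches no condition about study drug having stopped. It prohibits other treatment for NHL during the study (Section 3.6.2). Among the reasons for which a subject may be withdrawn from treatment it lists "Start of alternative anticancer therapy" (Section 3.8).

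**The concern.** The two classes in SAP 6.1.4 leave a gap. A lymphoma therapy that starts between first and last dose, both days included, is neither prior nor subsequent. If the efficacy sections take the term as defined, such a therapy has no effect on best overall response and none on the new-therapy censoring row.

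Three things are at stake. First, ORR is the Part 2 primary endpoint, and a response first seen after another lymphoma therapy would be credited to acalabrutinib. Second, progression-free time gained from that therapy would stay in PFS and DOR, contrary to Protocol 5.4; SAP Section 8, which lists changes from the protocol's analyses, does not mention this. Third, Table 1 uses two terms for what should be one date, so some subjects fit neither of its situations cleanly.

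**Working it through.** No figure in the plan depends on this definition, so there is nothing to reproduce. The check is a trace of the rules through one assumed subject, followed by the size of one misattributed response.

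**Inputs.** From the documents: Part 2 scans on Day 1 of Cycles 4, 7, 10 and 13 and then every 24 weeks (Protocol 4.1.22), which gives study days 85, 169, 253, 337, 505, 673 and 841; 30.4375 days per month (SAP 6); up to 40 subjects in Part 2 Cohort 1 (SAP 3.2); exact binomial 95% intervals (SAP 6). Assumed for illustration: other lymphoma therapy starts on day 150, last study drug dose is day 300, data cutoff is day 900, and scans continue on schedule.

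**1. Classification.** Subsequent requires start day > last-dose day. 150 > 300 is false, so the therapy is not subsequent. A start on day 300 also fails (300 > 300 is false). A start on day 301 passes.

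**2. Best overall response.** Suppose the first PR is on the day 253 scan. Under the SAP wording no subsequent therapy exists, the window stays open, and the subject is a responder. If the window closed at the actual start, 253 ≤ 150 is false and the PR would not count.

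**3. PFS without progression.** The new-therapy row is not triggered, so the data-cutoff row applies: censored at day 841, 841/30.4375 = 27.6 months. Under Protocol 5.4 the last assessment before day 150 is day 85: 85/30.4375 = 2.8 months.

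**4. PFS with progression on day 505.** There are two readings.
- If *alternative cancer therapy* in Situation 1 includes the day 150 therapy, the progression falls after the limit and is not an event. It must then be censored under Situation 2. The cutoff and study-exit rows require no progression, the new-therapy row requires a subsequent therapy, and the missed-visit row does not apply. No row gives a date.
- If *alternative* is read as *subsequent* in 6.1.4, the progression is an event at 505/30.4375 = 16.6 months, after other therapy.

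**5. Partial date.** If the day-150 start is recorded without its day and handled as a subsequent therapy under SAP 6.2.1, its imputed date precedes day 300 and is moved to day 301. It now counts as subsequent, but 301 − 150 = 151 days late. The day 253 PR still counts, and PFS without progression is censored at day 253 (253/30.4375 = 8.3 months), not day 85.

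**6. Size for ORR.** One response changes ORR by 1/40 = 2.5 points. With an assumed 18 true responders:

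| Responders | ORR | Exact 95% CI |
|---|---|---|
| 18/40 | 45.0% | 29.3–61.5 |
| 19/40 (1 extra) | 47.5% | 31.5–63.9 |
| 20/40 (2 extra) | 50.0% | 33.8–66.2 |

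**The case against.** The best answer is that the case should hardly arise. Protocol 3.6.2 prohibits chemotherapy, immunotherapy, experimental therapy and radiotherapy for NHL on study, so every affected subject would be a protocol deviation, and SAP 7.2 has the sponsor review important deviations before database lock. To change ORR, a subject must also have had no earlier response and then be scored PR or CR. Part 2 has no hypothesis test or power basis, and the illustrated intervals overlap heavily. This stands as a limit on size. It does not supply the missing rule: treated subjects stay in the all-treated analysis whether or not they deviated.

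Second, SAP 6.1.4 is introduced for the summaries, and neither 7.6.1 nor Table 1 cites it. That is correct, so applying it to efficacy is a reading. But it is the only definition of the word those sections use.

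Third, Situation 1 gives PFS and DOR some protection. A reader might infer that progression after on-treatment therapy is always counted as an event. The documents do not support that, because Situation 1 can be read to exclude it; what is missing then is a censoring date.

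Other stronger readings also fail. One might say that on-treatment therapy can never count as subsequent, but the partial-date rule can make it count, though late. One might take Protocol 3.8 as proof that new therapy precedes stopping study drug; it lists reasons and states no order. One might point to a new agent started in Part 3 while maintenance rituximab continues alone; the SAP wording would cover that, but the documents do not describe rituximab continuing after acalabrutinib has stopped.

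**Conclusion.** The point holds as a defect of definition. On the SAP's literal wording, a fully dated lymphoma therapy started from first dose through the day of last dose does not end the response window and does not trigger the new-therapy censoring row for PFS and DOR. For PFS and DOR this departs from Protocol 5.4 without being listed in SAP Section 8. For ORR the problem lies within the SAP's own window. Table 1 needs repair on either reading of its undefined term.

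The size is 2.5 points of Part 2 ORR for each response first reached after such therapy, at n = 40. The number of such subjects is not in the documents and is probably small because the therapy is prohibited; the one or two extra responders above are an assumption. A reader might infer that the Part 2 ORR will be materially inflated, but nothing in the documents shows that. The conclusion assumes that the analysis will apply 6.1.4 wherever the SAP says *subsequent anticancer therapy*.

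**What to change.** Leave SAP 6.1.3, 6.1.4 and 6.1.5 as they are. Redefining the term in 6.1.4 would also end the treatment-emergent period and the concomitant-medication window while a subject still takes study drug, and safety is the Part 3 primary objective.

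In SAP 7.6, add one term for efficacy only, *new anticancer therapy for lymphoma*: any non-protocol systemic therapy or radiotherapy given for the lymphoma under study and started on or after the first dose of any study drug, whether or not study drug has stopped. Exclude treatment of unrelated lesions or of other malignancies. Then:

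- use its start date in 7.6.1, 7.6.2 and both situations of Table 1, replacing the two terms now there;
- extend the new-therapy row so that any progression or death after that start is censored at the last adequate assessment before it;
- for this efficacy date, do not move a partial date to the day after last dose when the recorded month (or year, if only that is known) is earlier than that of last dose;
- list in SAP Section 8 any difference from Protocol 5.4 that remains.

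The cost is some SAP wording and one extra derivation. ORR, PFS and DOR may come out slightly less favourable. The case report form is not among the documents, so the sponsor should confirm that it records start dates for therapy begun on treatment.
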